5.4 Stratification

No stratification based on age, sex or other characteristics will be used in this trial.

5.5 Concomitant Medications/Vaccinations (Allowed & Prohibited)

If a subject does not discontinue all prior medications within 14 days or 5 half-lives of receiving the first dose of MK-3475, he/she may be included in the study if the investigator can rationalize that the specific use of a prior medication is not clinically relevant within the context of the trial.

Concurrent use of any prescription or non-prescription medication, or concurrent vaccination, during the course of the trial (i.e., after randomization or allocation) must first be discussed between the investigator and Sponsor Clinical Director prior to administration, unless appropriate medical care necessitates that therapy or vaccination should begin before the investigator and Sponsor Clinical Director can consult. The subject will be allowed to continue in the trial if both the Sponsor Clinical Director and the investigator agree.

5.5.1 Acceptable Concomitant Medications

All concomitant medication will be recorded on the case report form (CRF) including all prescription, over-the-counter (OTC), herbal supplements, and IV medications and fluids. If changes occur during the trial period, documentation of drug dosage, frequency, route, and date may also be included on the CRF.

All concomitant medications received within 28 days before screening and 30 days after the last dose of trial treatment should be recorded. Concomitant medications administered after 30 days after the last dose of trial treatment should be recorded for SAEs and ECIs as defined in Section 7.2.

Paracetamol/acetaminophen may be used for minor ailments without prior consultation with the investigator or the Sponsor Clinical Director.

Subjects receiving therapy with NSAIDS are permitted to continue this medication throughout the study, as clinically indicated. Subjects receiving other platelet aggregation inhibitors (e.g. Clopidogrel) may continue such medications, provided they are held for at least 5 days prior to pretreatment tumor biopsy and prior to surgical RCC resection, and are not restarted until at least the day following the procedure.

Medications or vaccinations specifically prohibited in the exclusion criteria are not allowed during the ongoing trial. If there is a clinical indication for any medication or vaccination specifically prohibited during the trial, discontinuation from trial therapy or vaccination may be required. The investigator should discuss any questions regarding this with the Sponsor Clinical Director. The final decision on any supportive therapy or vaccination rests with the investigator and/or the subject's primary physician. However, the decision to continue the subject on trial therapy or vaccination schedule requires the mutual agreement of the investigator, the Sponsor and the subject.

Prohibited Concomitant Medications

Subjects are prohibited from receiving the following therapies during the Screening and Treatment Phases of this trial:

- Anti-cancer systemic chemotherapy or biological therapy, other than the study prescribed administration of MK-3475
- Immunotherapy not specified in this protocol
- Chemotherapy not specified in this protocol
- Investigational agents other than MK-3475
- Radiation therapy

Note: Radiation therapy to a symptomatic lesion or to the brain may be considered on a case-by-case basis after consultation with the Sponsor. Such a radiated lesion should not be a RECIST 1.1 target lesion.

- Live vaccines within 30 days prior to screening and while participating in the trial. Examples of live vaccines include, but are not limited to, the following: measles, mumps, rubella, chicken pox, yellow fever, rabies, BCG, and typhoid (oral) vaccine. Seasonal influenza vaccines for injection are generally killed virus vaccines and are allowed; however intranasal influenza vaccines (e.g. Flu-Mist®) are live attenuated vaccines, and are not allowed.
- Systemic glucocorticoids, for any purpose other than to modulate AEs of suspected immunologic etiology or on the day of surgical RCC resection to modulate perioperative nausea.

Note: If systemic glucocorticoids are administered to a subject receiving MK-3475 during the neoadjuvant phase of the trial to modulate an AE of suspected immunologic etiology, the guidance in Section 5.2.1.2.1.1 should be followed with regard to continued MK-3475 administration.

- Anticoagulants, other than those administered by subcutaneous injection for deep vein thrombosis (DVT) prophylaxis in the perioperative and postoperative period. Prohibited anticoagulants include, but are not limited to heparin (iv), enoxaparin, and warfarin. Note: platelet aggregation inhibitors are permitted with certain restrictions (See Section 5.5.1).

Subjects who, in the assessment by the investigator, require the use of any of the aforementioned treatments for clinical management should be removed from the trial. Subjects may receive other medications that the investigator deems to be medically necessary.

Upon completion of the first visit in the follow-up phase of the trial (See Section 6- Trial Flow Chart), there are no prohibited therapies.

5.6 Rescue Medications & Supportive Care

All AEs are to be graded according to National Cancer Institute Common Terminology Criteria for Adverse Events (NCI CTCAE), version 4.0 (<http://ctep.cancer.gov>).

NOTE: RESCUE MEDICATION AND SUPPORTIVE CARE GUIDELINES SIGNIFICANTLY DIFFER BETWEEN THE NEOADJUVANT AND POST-RESECTION PHASES OF THIS TRIAL.

5.6.1 Supportive Care Guidelines During the Neoadjuvant Portion of this Trial

Subjects should receive appropriate supportive care measures as deemed necessary by the treating investigator including but not limited to the items outlined below:

- Diarrhea: Subjects should be carefully monitored for signs and symptoms of enterocolitis (such as diarrhea, abdominal pain, blood or mucus in stool, with or without fever) and of bowel perforation (such as peritoneal signs and ileus). In symptomatic subjects, infectious etiologies should be ruled out, and if symptoms are persistent and/or severe, endoscopic evaluation should be considered.
 - In subjects with severe enterocolitis (Grade 3-4), neoadjuvant MK-3475 treatments will be discontinued and treatment with systemic corticosteroids should be initiated at a dose of 1 to 2 mg/kg/day of prednisone or equivalent. When symptoms improve to Grade 1 or less, corticosteroid taper should be started and continued over at least 1 month.
 - In subjects with moderate enterocolitis (Grade 2), neoadjuvant MK-3475 will be discontinued and anti-diarrheal treatment should be started. If symptoms are persistent for more than one week, systemic corticosteroids should be initiated (e.g., 0.5 mg/kg/day of prednisone or equivalent). When symptoms improve to Grade 1 or less, corticosteroid taper should be started and continued over at least 1 month.
 - All subjects who experience diarrhea should be advised to drink liberal quantities of clear fluids. If sufficient oral fluid intake is not feasible, fluid and electrolytes should be substituted via IV infusion.
- Nausea/vomiting: Nausea and vomiting should be treated aggressively, and consideration should be given in subsequent cycles to the administration of prophylactic antiemetic therapy according to standard institutional practice. Subjects should be strongly encouraged to maintain liberal oral fluid intake.
- Anti-infectives: Subjects with a documented infectious complication should receive oral or IV antibiotics or other anti-infective agents as considered appropriate by the treating investigator for a given infectious condition, according to standard institutional practice.
- Immune-related adverse events: Please see Section 5.6.1.1 below and the separate guidance document in the Administrative binder regarding diagnosis and management of adverse experiences of a potential immunologic etiology.

- Management of Infusion Reactions: Acute infusion reactions (which can include cytokine release syndrome, angioedema, or anaphylaxis) are different from allergic/hypersensitive reactions, although some of the manifestations are common to both AEs. Signs and symptoms usually develop during or shortly after drug infusion and generally resolve completely within 24 hours of completion of infusion. Signs/symptoms may include: Allergic reaction/hypersensitivity (including drug fever); Arthralgia (joint pain); Bronchospasm; Cough; Dizziness; Dyspnea (shortness of breath); Fatigue (asthenia, lethargy, malaise); Headache; Hypertension; Hypotension; Myalgia (muscle pain); Nausea; Pruritis/itching; Rash/desquamation; Rigors/chills; Sweating (diaphoresis); Tachycardia; Tumor pain (onset or exacerbation of tumor pain due to treatment); Urticaria (hives, welts, wheals); Vomiting.

Table 5 below shows treatment guidelines for subjects who experience an infusion reaction associated with administration of MK-3475 during the neoadjuvant phase of this study.

Table 5 Infusion Reaction Treatment Guidelines-Neoadjuvant MK-3475 Only

| NCI CTCAE Grade | Treatment | Premedication at Subsequent Dosing |
|---|--|--|
| Grade 1 Mild reaction; infusion interruption not indicated; intervention not indicated | Increase monitoring of vital signs as medically indicated until the subject is deemed medically stable in the opinion of the investigator. | None |
| Grade 2 Requires infusion interruption but responds promptly to symptomatic treatment (e.g., antihistamines, NSAIDS, narcotics, IV fluids); prophylactic medications indicated for ≤ 24 hrs. | Stop Infusion. Additional appropriate medical therapy may include but is not limited to: IV fluids Antihistamines NSAIDS Acetaminophen Narcotics Increase monitoring of vital signs as medically indicated until the subject is deemed medically stable in the opinion of the investigator. If symptoms resolve within one hour of stopping drug infusion, the infusion may be restarted at 50% of the original infusion rate (e.g. from 100 mL/hr to 50 mL/hr). Otherwise dosing will be held until symptoms resolve and the subject should be premedicated for the next scheduled dose. Subjects who develop Grade 2 toxicity should be permanently discontinued from further neoadjuvant MK-3475 administration. | No subsequent neoadjuvant MK-3475 dosing. Subject should proceed to SOC RCC resection. Only for subjects with known metastatic disease at the time of RCC resection: If post-resection MK-3475 is to be subsequently administered, subject may be premedicated 1.5h (± 30 minutes) prior to infusion of pembrolizumab (MK-3475) with: Diphenhydramine 50 mg po (or equivalent dose of antihistamine). Acetaminophen 500-1000 mg po (or equivalent dose of antipyretic). |

| NCI CTCAE Grade | Treatment | Premedication at Subsequent Dosing |
|--|---|------------------------------------|
| Grades 3 or 4 | | |
| Grade 3: Prolonged (i.e., not rapidly responsive to symptomatic medication and/or brief interruption of infusion); recurrence of symptoms following initial improvement; hospitalization indicated for other clinical sequelae (e.g., renal impairment, pulmonary infiltrates) | Stop Infusion. Additional appropriate medical therapy may include but is not limited to: IV fluids Antihistamines NSAIDS Acetaminophen Narcotics Oxygen Pressors Corticosteroids Epinephrine | No subsequent dosing |
| Grade 4: Life-threatening; pressor or ventilatory support indicated | Increase monitoring of vital signs as medically indicated until the subject is deemed medically stable in the opinion of the investigator. Hospitalization may be indicated. Subject is permanently discontinued from further MK-33475 administration. | |
| Appropriate resuscitation equipment should be available in the room and a physician readily available during the period of drug administration. For Further information, please refer to the Common Terminology Criteria for Adverse Events v4.0 (CTCAE) at http://ctep.cancer.gov | | |

5.6.1.1 Supportive Care Guidelines for Events of Clinical Interest (ECIs) and Immune-Related Adverse Events (irAEs) During Neoadjuvant MK-3475 Only

Events of clinical interest of a potential immunologic etiology may be defined as an adverse event of unknown etiology, associated with drug exposure and is consistent with an immune phenomenon. irAEs may be predicted based on the nature of MK-3475, its mechanism of action, and reported experience with immunotherapies that have a similar mechanism of action. Special attention should be paid to AEs that may be suggestive of potential irAEs. An irAE can occur shortly after the first dose or several months after the last dose of treatment.

If an irAE is suspected, efforts should be made to rule out neoplastic, infectious, metabolic, toxin or other etiologic causes prior to labeling an adverse event as an irAE. Subjects who develop a Grade 2 or higher irAEs should be discussed immediately with the Sponsor.

Recommendations for managing irAEs during the neoadjuvant phase of the trial that are not detailed elsewhere in the protocol are detailed in [Table 6](#).

Table 6 General Approach to Handling irAEs- **Neoadjuvant Phase Only**

| irAE | Discontinue study treatments? | Supportive Care |
|---------------------|--|--|
| Grade 1 | No action | Provide symptomatic treatment. |
| Grade 2 | Discontinue neoadjuvant MK-3475 treatment. | Consider systemic corticosteroids in addition to appropriate symptomatic treatment. |
| Grade 3 and Grade 4 | Discontinue neoadjuvant MK-3475 treatment. | Systemic corticosteroids are indicated in addition to appropriate symptomatic treatment. May utilize 1 to 2 mg/kg prednisone or equivalent per day. Steroid taper should be considered once symptoms improve to Grade 1 or less and tapered over at least 4 weeks. |

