5.2.1.2 Dose Modification and Toxicity Management Guidelines for Pembrolizumab

Dose modification and toxicity management for immune-related AEs associated with pembrolizumab

AEs associated with pembrolizumab exposure may represent an immunologic etiology. These immune-related AEs (irAEs) may occur shortly after the first dose or several months after the last dose of pembrolizumab treatment and may affect more than one body system simultaneously. Therefore, early recognition and initiation of treatment is critical to reduce complications. Based on existing clinical trial data, most irAEs were reversible and could be managed with interruptions of pembrolizumab, administration of corticosteroids and/or other supportive care. For suspected irAEs, ensure adequate evaluation to confirm etiology or exclude other causes. Additional procedures or tests such as bronchoscopy, endoscopy, skin biopsy may be included as part of the evaluation. Based on the severity of irAEs, withhold or permanently discontinue pembrolizumab and administer corticosteroids. Dose modification and toxicity management guidelines for irAEs associated with pembrolizumab are provided in [Table 6](#) for neoadjuvant dosing and [Table 3](#) for post-resection dosing.

5.2.1.2.1.1 Neoadjuvant MK-3475

Based on the first interim analysis of lymphocytic infiltrates in tumors resected from the first 9 subjects, if an increase in tumor lymphocytic infiltration of 2-fold or greater is not observed in more than one of the 6 subjects in this group that received a 2 dose course of neoadjuvant

MK-3475, all subsequent subjects enrolled in this trial may be treated with 3 doses of MK-3475. Details are described in Section 8.0 – Statistical Analysis Plan.

Administration of neoadjuvant MK-3475 during this trial must be discontinued for drug-related toxicities above Grade 1 in severity and for severe or life-threatening AEs as described in Section 5.6.1. Such subjects should proceed with SOC surgical RCC resection as soon as they have sufficiently recovered from the AE to undergo this procedure.

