For subjects without metastatic disease at the time of surgical RCC resection who experience drug-related toxicities above Grade 1 during neoadjuvant treatment, post-resection MK-3475 should also not be administered and the subject should be permanently discontinued. However, subjects with known metastatic disease at the time of surgical RCC resection who develop Grade 2 or greater drug-related AEs during neoadjuvant MK-3475 treatment may still be eligible to receive post-resection MK-3475 if the drug-related AE severity as listed in [Table 3](#) below does not prescribe permanent treatment discontinuation.

5.2.1.2.1.2 Post-Resection MK-3475

Post-resection administration of MK-3475 must be withheld for drug-related toxicities and severe or life-threatening AEs as per [Table 3](#) below. See Section 5.6.2 for supportive care guidelines, including use of corticosteroids to be followed during post-resection administration of MK-3475 (only applicable in the Post-Resection Phase of the study).

Table 3 Dose Modification and Toxicity Management Guidelines for Immune-related AEs Associated with Pembrolizumab (During Post-Resection Phase ONLY)

| General instructions: | | | | |
|------------------------------|---|--------------------------------------|---|--|
| Immune-related AEs | Toxicity grade or conditions (CTCAEv4.0) | Action taken to pembrolizumab | irAE management with corticosteroid and/or other therapies | Monitor and follow-up |
| Pneumonitis | Grade 2 | Withhold | 
 Administer corticosteroids (initial dose of 1-2 mg/kg prednisone or equivalent) followed by taper | 
 Monitor participants for signs and symptoms of pneumonitis Evaluate participants with suspected pneumonitis with radiographic imaging and initiate corticosteroid treatment Add prophylactic antibiotics for opportunistic infections |
| | Grade 3 or 4, or recurrent Grade 2 | Permanently discontinue | | |

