| Grade 2 Requires therapy or infusion interruption but responds promptly to symptomatic treatment (e.g., antihistamines, NSAIDs, narcotics, IV fluids); prophylactic medications indicated for ≤ 24 hrs | Stop Infusion. Additional appropriate medical therapy may include but is not limited to: IV fluids Antihistamines NSAIDs Acetaminophen Narcotics Increase monitoring of vital signs as medically indicated until the subject is deemed medically stable in the opinion of the investigator. If symptoms resolve within 1 hour of stopping drug infusion, the infusion may be restarted at 50% of the original infusion rate (e.g. from 100 mL/hr to 50 mL/hr). Otherwise dosing will be held until symptoms resolve and the subject should be premedicated for the next scheduled dose. Subjects who develop Grade 2 toxicity despite adequate premedication should be permanently discontinued from further study drug treatment | Subject may be premedicated 1.5h (\pm 30 minutes) prior to infusion of _____ with: Diphenhydramine 50 mg po (or equivalent dose of antihistamine). Acetaminophen 500-1000 mg po (or equivalent dose of analgesic). |

| NCI CTCAE Grade | Treatment | Premedication at Subsequent Dosing |
|--|---|------------------------------------|
| Grades 3 or 4 Grade 3: Prolonged (i.e., not rapidly responsive to symptomatic medication and/or brief interruption of infusion); recurrence of symptoms following initial improvement; hospitalization indicated for other clinical sequelae (e.g., renal impairment, pulmonary infiltrates) Grade 4: Life-threatening; pressor or ventilatory support indicated | Stop Infusion. Additional appropriate medical therapy may include but is not limited to: Epinephrine** IV fluids Antihistamines NSAIDs Acetaminophen Narcotics Oxygen Pressors Corticosteroids Increase monitoring of vital signs as medically indicated until the subject is deemed medically stable in the opinion of the investigator. Hospitalization may be indicated. **In cases of anaphylaxis, epinephrine should be used immediately. Subject is permanently discontinued from further study drug treatment. | No subsequent dosing |

Appropriate resuscitation equipment should be available at the bedside and a physician readily available during the period of drug administration.

For further information, please refer to the Common Terminology Criteria for Adverse Events v4.0 (CTCAE) at <http://ctep.cancer.gov>

Other allowed dose interruption for pembrolizumab

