5.8 Subject Withdrawal/Discontinuation Criteria

Subjects may withdraw consent at any time for any reason or be dropped from the trial at the discretion of the investigator should any untoward effect occur. In addition, a subject may be withdrawn by the investigator or the Sponsor if enrollment into the trial is inappropriate, the trial plan is violated, or for administrative and/or other safety reasons. Specific details regarding discontinuation or withdrawal procedures; including specific details regarding withdrawal from Future Biomedical Research, are provided in Section 7.1.4 – Other Procedures.

Discontinuation from treatment is “permanent”. Once a subject is discontinued, he/she shall not be allowed to restart treatment.

A subject must be discontinued from the trial for any of the following reasons:

- The subject or legal representative (such as a parent or legal guardian) withdraws consent.
- For subjects who have declined a study-prescribed pre-treatment core needle biopsy but instead have undergone a diagnostic biopsy performed as per local SOC from which tissue will be submitted, this biopsy was not performed within 45 days prior to the first dose of MK-3475 or tissue submitted is not sufficient for the specified study-related analyses.
- The subject, if randomized to receive neoadjuvant MK-3475, interrupts neoadjuvant trial medication administration for more than 7 consecutive days or 1 cumulative missed dose.
- The subject has a medical condition or personal circumstance which, in the opinion of the investigator and/or Sponsor, places the subject at unnecessary risk through continued participation in the trial or does not allow the subject to adhere to the requirements of the protocol.
- The subject has a confirmed positive serum pregnancy test.
- In subjects assigned to receive neoadjuvant MK-3475, histologic analysis of the pre-treatment core needle biopsy does not confirm the diagnosis of RCC with one or more clear cell components present.
- In all subjects, histologic examination of the surgically excised tumor tissue does not confirm the diagnosis of RCC with clear cell elements.
- In subjects assigned to receive neoadjuvant MK-3475, the patient does not undergo surgical RCC resection within 5 weeks of the final dose of MK-3475.

- In subjects assigned to the control group (no neoadjuvant MK-3475), the patient fails to undergo surgical RCC resection within 6 weeks of randomization.

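### Table 5 tells sites to premedicate for a further dose after an unresolved Grade 2 infusion reaction, while its next sentence, its third column and Section 5.2.1.2.1.1 end neoadjuvant dosing

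*Combined protocol and SAP*

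**What the plan says.** Four statements cover a Grade 2 infusion reaction during neoadjuvant MK-3475.

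- **Table 5, Grade 2 row, Treatment column.** If symptoms clear within an hour of stopping, the infusion may resume at half speed. For the remaining cases: "Otherwise dosing will be held until symptoms resolve and the subject should be premedicated for the next scheduled dose".
- **Same cell, next sentence.** "Subjects who develop Grade 2 toxicity should be permanently discontinued from further neoadjuvant MK-3475 administration".
- **Same row, third column.** "No subsequent neoadjuvant MK-3475 dosing. Subject should proceed to SOC RCC resection". It then covers premedication before post-resection MK-3475, for subjects with known metastatic disease only.
- **Section 5.2.1.2.1.1.** "Administration of neoadjuvant MK-3475 during this trial must be discontinued for drug-related toxicities above Grade 1 in severity". For subjects without metastatic disease at resection who had such toxicity, it adds that "post-resection MK-3475 should also not be administered and the subject should be permanently discontinued".

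The post-resection counterpart, Table 8 in Section 5.6.2, repeats the hold-and-premedicate sentence but follows it with: "Subjects who develop Grade 2 toxicity despite adequate premedication should be permanently discontinued from further study drug treatment".

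Section 7.1.1.8 requires the investigator and the sponsor to consult on any interruption of neoadjuvant dosing and to document their joint decision.

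**The concern.** The two sentences in the Treatment cell are adjacent, apply to the same patients and lead to opposite actions for the next neoadjuvant dose. Staff turn to that column while a reaction is being managed. If they act on the first sentence, the patient is premedicated and may be dosed again. If they act on the second, the patient receives no more neoadjuvant drug and goes to surgery. Nothing in the protocol says which sentence takes precedence.

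At stake is consistent handling of a safety event in a trial whose first primary objective is the safety of neoadjuvant MK-3475. Two sites could each follow a sentence of the protocol to the letter and treat the same event differently.

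**Working it through.** No arithmetic applies. The check is whether any reading of the hold-and-premedicate sentence fits the other statements.

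**Step 1: which patients it covers.** The sentence begins with Otherwise and follows the provision for symptoms that clear within one hour. It therefore applies to Grade 2 reactions outside that provision, chiefly those not resolved within the hour. It does not apply to every Grade 2 reaction.

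**Step 2: read the scheduled dose as the next neoadjuvant dose.** This is the natural reading, because the table's title limits it to the neoadjuvant phase. A reaction at dose 1 of 2 (or at dose 1 or 2 of 3, if the longer course is adopted) would then lead to a premedicated further dose. Compare:

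| Statement | Further neoadjuvant dose? |
|---|---|
| Table 5, Treatment, hold and premedicate | Yes, after premedication |
| Table 5, Treatment, next sentence | No |
| Table 5, third column | No |
| Section 5.2.1.2.1.1, drug-related toxicity above Grade 1 | No |

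One statement conflicts with three.

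**Step 3: read the scheduled dose as the first post-resection dose.** For subjects with known metastatic disease this fits the third column, which allows premedication before post-resection drug. For subjects without metastatic disease it fails: Section 5.2.1.2.1.1 withholds post-resection MK-3475 after drug-related toxicity above Grade 1. The sentence is not restricted to metastatic subjects, so this reading removes the conflict for only part of the population it covers.

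**Step 4: compare Table 8.** There the sequence is hold, premedicate, and stop if a Grade 2 reaction occurs even with premedication. The stop is conditional on the premedicated dose having been given, so the two sentences describe consecutive steps. In Table 5 the stop sentence has no such condition and applies at the first Grade 2 event. That missing condition is why the same pair of sentences is compatible in Table 8 and contradictory in Table 5.

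**Result.** On neither reading is the sentence consistent with the other passages for all the subjects it covers.

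**The case against.** The strongest reply is that the overall message is hard to miss. Three of the four statements end neoadjuvant dosing, and the Grade 2 entries for enterocolitis in Section 5.6.1, immune-related events in Table 6 and pneumonitis in Table 7 follow the same pattern. A site reading the whole row together with Section 5.2.1.2.1.1 would see one outlying clause. Section 7.1.1.8 adds a safeguard, since a held dose should bring the sponsor into the decision.

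Much of this stands, and it limits the practical risk. It does not remove the contradiction. The outlying clause is an explicit instruction in the Treatment column, and consultation under Section 7.1.1.8 does not tell either party which sentence governs.

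A reader might also infer that the half-speed restart conflicts with the stop rule. The text does not require that. The restart concerns the infusion already under way, whereas the stop sentence in Table 5 concerns further administration, and on an ordinary reading both can be followed.

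**Conclusion.** The point holds as an internal contradiction confined to one branch of one table row: Grade 2 reactions during neoadjuvant dosing that fall under the Otherwise sentence, with at least one neoadjuvant dose still planned. The instruction for the next neoadjuvant dose cannot be followed as written. The possible consequence is re-exposure of a patient whom the other passages stop.

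The number of patients cannot be estimated, because the documents give no rate for Grade 2 infusion reactions or for those unresolved at one hour. It may be low: Table 5 itself describes Grade 2 reactions as responding promptly to treatment. The conclusion assumes that a reaction managed under Table 5 counts as drug-related for Section 5.2.1.2.1.1. The conflict within the table row does not need that assumption.

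A reader might infer that the wording also decides whether a patient stays in the pharmacodynamic analysis, since Section 5.8 discontinues a subject who "interrupts neoadjuvant trial medication administration for more than 7 consecutive days or 1 cumulative missed dose". The documents do not establish this. The Per-Protocol definition in Section 8.2.3 refers to exposure but sets no minimum number of doses and does not exclude subjects discontinued under Section 5.8. Subjects stopped for toxicity still go to resection, and replacement is possible under Section 5.9. Section 4.2.3.2 mentions tissue from subjects given a full course, which lends the inference some support but is not an exclusion rule. Rewording Table 5 would not settle how partly dosed subjects are counted, so no loss from the denominator is claimed here.

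**What to change.** Reconcile the hold-and-premedicate sentence in the Grade 2 row of Table 5 with the sentence after it, with the third column of the row and with Section 5.2.1.2.1.1, so that a single instruction remains for later neoadjuvant doses. State explicitly whether the scheduled dose in that sentence is a neoadjuvant or a post-resection dose and, if the latter, for which subjects. The choice of instruction is for the sponsor's clinical team; this review proposes none.

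The cost is protocol wording, plus notice to sites and correction of any site material that reproduces the table. Sample size, visits and analyses are unchanged.
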